The primary endpoint is to evaluate the **safety and tolerability** of concurrent single/low dose radiotherapy (8 Gy/1fx) in combination with pembrolizumab in relapsed and/or refractory myeloma patients at 3 months (**acute toxicity, primary endpoint**) and at 6 and 12 months (**late toxicity**). The secondary objective is to characterize the effect of radiation in combination with pembrolizumab on systemic response rates using international myeloma working group (IMWG) uniform response criteria for myeloma, to assess baseline changes in PET/CT as a result of combining pembrolizumab and radiotherapy, and to evaluate treatment response at irradiated and un-irradiated sites (i.e. the abscopal effect) using baseline PET/CT. Exploratory analysis would include analyzing Circulating Myeloma Tumor cells and phenotype of T cells as a prognostic and predictive biomarker. Compare blood Myeloma tumor cells with BM tumor cells. We are interested in comparing T cell phenotype after each treatment and using that as a prognostic biomarker. We will also evaluate serum LDH, CRP, ESR, ALC, cytokines and chemokines (such as IL-6, s IL-6R) and other immune related biomarkers, and correlate their expression pre and post treatment and evaluate changes in bone marrow biopsy and peripheral blood for mutational load, mutational signature (whole exome sequencing), transcriptome of the T cells, mutation specific T cells, PD1 and PDL1 expression on MM cells and T cells by flow/IHC, RNA-seq. Other biomarker correlative exploratory analysis (role of exosomes, etc) may also be pursued as ancillary research to this trial;

2. Acute Toxicity and Late Toxicity Assessment:

[figure not shown]
Acute toxicity (i.e. > Grade 2 CTCAE toxicity at **3 months**) associated with radiation therapy at the **radiated site** will be analyzed as the **primary safety endpoint** in this pilot study; Goal would be to see less than 20% > grade 2 toxicity at 3 months within the radiated area.

CTCAE criteria (see Appendix I) will be applied to assess acute toxicity.

Other endpoints that may be analyzed include late toxicity (> Grade 2 CTCAE toxicity at the radiated site at **6 months and 12 months**), systemic response against myeloma burden to localized radiation and pembrolizumab using IMWG uniform criteria, as well as other endpoints (defined in more detail in section 3.0).

3. Trial Schema

Figure 1: Trial Overview

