3. OBJECTIVES, ENDPOINTS & HYPOTHESES

1. Primary Objective, Endpoint, & Hypothesis

Primary Objective

To evaluate the safety of concurrent single/low dose radiotherapy (**8 Gy/1fx**) in combination with Pembrolizumab in relapsed or refractory myeloma patients; **Once 10 patients are enrolled, we will stop trial for 3 months to assess for acute toxicity, and then resume the trial.**

Primary Endpoint

CTCAE > grade 2 toxicity at the specific irradiated **organ site at 3 months** (the Dose Limiting Toxicity);

Primary Hypothesis

The primary hypothesis of this pilot study is that the use of concomitant Pembrolizumab and radiation therapy in multiple myeloma patients will be well tolerated and safe.

Alternative Hypothesis

It is possible that concurrent use of radiotherapy and Pembrolizumab in relapsed/refractory myeloma may increase CTCAE > grade 2 toxicity within the radiated site at 3 months.

2. Secondary Objective(s), Endpoint(s) & Hypothesis (es)

Secondary Objectives

To characterize late toxicity (CTCAE > grade 2 toxicity at **6 and 12 months**) and the effect of radiation in combination with Pembrolizumab on systemic response rates using international myeloma working group (IMWG) uniform response criteria for multiple myeloma at **6 months and 12 months**;

To assess changes in PET/CT as a result of combining Pembrolizumab and radiotherapy at **6 months and 12 months**;

Secondary Endpoints

- a. 1. Number of patients achieving any response (from baseline) per IMWG response criteria at **6 months and 12 months**;
- b. 2. Overall survival time at **6 months and 12 months**;
- c. 3. Overall response based on baseline changes on PET/CT at **6 months and 12 months**;
- d. 4. Difference in pre and post treatment serum immune biomarkers;

Secondary Endpoint Definitions

- a. Response is defined per IMWG criteria, and will be calculated at **6 months and 12 months**;
- b. Overall survival will be defined as time from first treatment on cycle 1, day 1 to the earlier of date of death and/or last follow up at **6 months and 12 months**.
- c. Overall response will be defined using IMWG uniform response criteria.
- d. Several serum biomarkers will be analyzed.

Secondary Hypotheses

The secondary hypothesis is that low dose/single fraction (8Gy/1fx) will synergize with Pembrolizumab for a more effective anti-myeloma response per IMWG, via the radiation induced abscopal response.

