- Female subject of childbearing potential should be willing to use 2 methods of birth control or be surgically sterile, or abstain from heterosexual activity for the course of the study through 120 days after the last dose of study medication. Subjects of child bearing potential are those who have not been surgically sterilized or have been free from menses for > 1 year.
- Male subject should agree to use an adequate method of contraception starting with the first dose of study therapy through 120 days after the last dose of study therapy.
- Does not have a history or current evidence of any condition, therapy, or laboratory abnormality that might interfere with the subject's participation for the full duration of the trial or is not in the best interest of the subject to participate, in the opinion of the treating investigator.

Subjects who restart treatment will be retreated at the same dose and dose interval as when they last received pembrolizumab. Treatment will be administered for up to one additional year.

Visit requirements are outlined in Section 9.0 – Trial Flow Chart.

Survival Follow-up

Once a subject experiences confirmed disease progression or starts a new anti-cancer therapy, the subject moves into the survival follow-up phase and should be contacted by telephone every 12 weeks to assess for survival status until death, withdrawal of consent, or the end of the study, whichever occurs first.

Assessing and Recording Adverse Events

An adverse event is defined as any untoward medical occurrence in a patient or clinical investigation subject associated with the use of a test article and which does not necessarily have to have a causal relationship with this treatment. An adverse event can therefore be any unfavorable and unintended sign (including an abnormal laboratory finding, for example), symptom, or disease temporally associated with the use of a medicinal product or protocol-specified procedure, whether or not considered related to the medicinal product or protocol-specified procedure. Any worsening (i.e., any clinically significant adverse change in frequency and/or intensity) of a preexisting condition that is temporally associated with the use of the Merck's product or radiotherapy, is also an adverse event.

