Changes resulting from normal growth and development that do not vary significantly in frequency or severity from expected levels are not to be considered adverse events. Examples of this may include, but are not limited to, teething, typical crying in infants and children and onset of menses or menopause occurring at a physiologically appropriate time.

Merck product includes any pharmaceutical product, biological product, device, diagnostic agent or protocol-specified procedure, whether investigational (including placebo or active comparator medication) or marketed, manufactured by, licensed by, provided by or distributed by Merck for human use.

Adverse events may occur during the course of the use of Merck product or SRS in clinical trials or within the follow-up period specified by the protocol, or prescribed in clinical practice, from overdose (whether accidental or intentional), from abuse and from withdrawal.

Adverse events may also occur in screened subjects during any pre-allocation baseline period as a result of a protocol-specified intervention, including washout or discontinuation of usual therapy, diet, placebo treatment or a procedure.

Progression of the cancer under study is not considered an adverse event unless it is considered to be drug related by the investigator.

All adverse events that occur after the consent form is signed but before treatment allocation/randomization must be reported to Merck and the PI by the investigator if they cause the subject to be excluded from the trial, or are the result of a protocol-specified intervention, including but not limited to washout or discontinuation of usual therapy, diet, placebo treatment or a procedure.

From the time of treatment allocation/randomization through 30 days following cessation of treatment, all adverse events must be documented by the investigator. Such events will be

recorded at each examination on the Adverse Event case report forms/worksheets. The reporting timeframe for adverse events meeting any serious criteria is described in section 9 and 10. The investigator will make every attempt to follow all subjects with non-serious adverse events for outcome.

Definition of an Overdose for This Protocol and Reporting of Overdose to the Sponsor and to Merck

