For the time period beginning at treatment allocation/randomization through 90 days following cessation of treatment, or 30 days following cessation of treatment if the subject initiates new anticancer therapy, whichever is earlier, any ECI, or follow up to an ECI, whether or not related to Merck product, must be reported within 24 hours to the Sponsor and within 24 hours to Merck Global Safety.

Events of clinical interest for this trial include:

1. an overdose of Merck product, as defined in Section 11 - Definition of an Overdose for This Protocol and Reporting of Overdose to the Sponsor, that is not associated with clinical symptoms or abnormal laboratory results.
2. an elevated AST or ALT lab value that is greater than or equal to 3X the upper limit of normal and an elevated total bilirubin lab value that is greater than or equal to 2X the upper limit of normal and, at the same time, an alkaline phosphatase lab value that is less than 2X the upper limit of normal, as determined by way of protocol-specified laboratory testing or unscheduled laboratory testing.*

*Note: These criteria are based upon available regulatory guidance documents. The purpose of the criteria is to specify a threshold of abnormal hepatic tests that may require an additional evaluation for an underlying etiology.

4. Protocol-Specific Exceptions to Serious Adverse Event Reporting

Efficacy endpoints as outlined in this section will not be reported to Merck as described section related to "Immediate Reporting of Adverse Events to the Sponsor and to Merck", unless there

is evidence suggesting a causal relationship between the drug and the event. Any such event will be submitted to the Sponsor within 24 hours and to Merck Global Safety within 2 working days either by electronic or paper media.

Specifically, the suspected/actual events covered in this exception include any event that is disease progression of the cancer under study.

The Sponsor will monitor unblinded aggregated efficacy endpoint events and safety data to ensure the safety of the subjects in the trial. Any suspected endpoint which upon review is not progression of the cancer under study will be forwarded to Merck Global Safety as a SAE within 2 working days of determination that the event is not progression of the cancer under study

Hospitalization related to convenience (e.g. transportation issues etc.) will not be considered a SAE.

Evaluating Adverse Events

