11. STATISTICAL ANALYSIS PLAN

1. Statistical Analysis Plan Summary

Study Design

The study is a pilot study to look at the safety of concurrent PD-1 inhibitor and SRS for relapsed/refractory myeloma. A total of 24 patients will be enrolled on the trial (20 is the minimum, with an additional 4 patients, to make for any attrition and/or loss to follow-up). 12 patients will be allowed to not have measurable myeloma disease in this trial. Once 10 patients are enrolled, we will stop trial for 3 months to assess for acute toxicity, and then resume the trial. The estimated exact Clopper-Pearson 95% confidence interval for a 20% rate based on 5 responses in 20 patients is (0.087, 0.491), with a precision of 0.185. If we see lower than 20% difference in rate of toxicity at 3 months, the combination will be deemed safe.

A minimum of 20 patients are required to complete full treatments. An additional 20% is allowed for drop out/failure to adhere to required follow-up and treatment recommendations. Thus, 24 patients will be allowed to be enrolled on the trial to make for any attrition and/or loss to follow-up. 12 patients will be allowed to not have measurable myeloma disease.

# of Responses / # of Patients	95% confidence interval
5 / 20	(0.087, 0.491)
6 / 24	(0.098, 0.467)

Populations for analysis

- Enrolled set: All subjects who signed an informed consent.
- Safety set: All subjects who received at least one dose of any study drug.
- Full analysis set: All subjects from the safety set who have the required follow-up and treatment adherence to evaluate response and safety over time.

2. Statistical Analyses

1. Response

IMWG criteria will be used to assess response. Proportion of patients achieving stable

disease or better will be reported at **6 months** and **12 months**; Response rates will be reported along with 95% confidence intervals will be estimated using the Clopper-Pearson method.

2. Safety

Proportion of acute (at **3 months**) and late toxicity (**6 and 12 months**) will be reported, and 95% confidence intervals will be estimated using the Clopper-Pearson method.

3. Overall Survival

For overall survival, death from any cause will be defined as the event. Patients will be censored at time of last follow-up. OS will be estimated using the Kaplan-Meier product-limit method. Overall survival will be analyzed at **6 months, and 12 months**.

4. Biological variables

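### The progression exemption from adverse events is lifted only for a link to the drug, not to radiotherapy, although the primary endpoint is toxicity at an irradiated myeloma lesion

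*Combined protocol and SAP*

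**What the plan says.** Section 3 defines the primary endpoint as "CTCAE > grade 2 toxicity at the specific irradiated" organ site at 3 months. Section 2 sets the target: "Goal would be to see less than 20% > grade 2 toxicity at 3 months within the radiated area". The statistical analysis plan (Section 11) turns this into a verdict: "If we see lower than 20% difference in rate of toxicity at 3 months, the combination will be deemed safe".

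Section 10, under Assessing and Recording Adverse Events, first gives a broad definition. A clinically significant worsening of an existing condition, if "temporally associated with the use of the Merck's product or radiotherapy, is also an adverse event". It then makes an exception: "Progression of the cancer under study is not considered an adverse event unless it is considered to be drug related by the investigator".

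The exceptions to serious adverse event reporting, later in Section 10, follow the same pattern. Efficacy endpoints are not reported to the drug manufacturer unless there is evidence that the drug caused the event, and the scope is stated as: "Specifically, the suspected/actual events covered in this exception include any event that is disease progression of the cancer under study". The causality row of Table 6 asks only about the manufacturer's product.

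Section 8 (Radiation Toxicity Evaluation) is broader. For a suspected novel or unexpected toxicity of grade 3 or higher it asks, where possible, whether immune therapy, radiotherapy or the combination is responsible, with attribution recorded for each. The flow chart in Section 9 schedules CTCAE grading of the irradiated site at 3, 6 and 12 months.

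**The concern.** The radiation target is the tumour. Section 8 defines the gross tumour volume as the lytic or extra-osseous lesion, and Section 2 admits symptomatic lesions. Pain, fracture or swelling in the field within 3 months can therefore be read as treatment injury or as progression of that lesion. The label matters, because progression leaves the adverse event definition and returns only if it is linked to the drug. A link to radiotherapy, the other half of the tested treatment, does not restore it.

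The analysis plan says only that the proportion with acute toxicity will be reported with an exact interval. It does not say whether the count comes from the adverse event records or the separate site assessment, or how an in-field event attributed to progression is counted. The trial is open-label, the investigator makes the call, and the documents describe no independent adjudication of it. At stake is the one rate on which the combination is declared safe.

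**Working it through.** **Step 1. The clauses side by side.**

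| Place | What it covers | Is radiotherapy named? |
|---|---|---|
| Section 10, general adverse event definition | Worsening associated in time with the product or radiotherapy | Yes |
| Section 10, progression exemption | Progression, unless linked to the drug | No |
| Section 10, exception to serious event reporting | Progression, unless caused by the drug | No |
| Section 10, Table 6 causality row | Manufacturer's product | No |
| Section 8, attribution of novel or unexpected grade 3+ toxicity | Immune therapy, radiotherapy, combination | Yes |

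*Drug* cannot be stretched to include the radiation. Section 10 counts a procedure as the manufacturer's product only if the manufacturer makes, licenses, provides or distributes it.

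**Step 2. What the wording removes.** Take a new event above grade 2 in the irradiated lesion.

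- Called toxicity: an adverse event, whatever its cause.
- Called progression, linked to the drug: an adverse event.
- Called progression, linked to the combination: arguably an adverse event, since the drug is part of the cause.
- Called progression, linked to radiotherapy alone: not an adverse event.

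Only the last case is removed by the text itself. A toxicity wrongly called progression can also be lost, but that is an investigator's error, not the protocol's instruction.

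**Step 3. The plan's own figures.** Two-sided 95% Clopper-Pearson limits are the 0.025 quantile of Beta(x, n−x+1) and the 0.975 quantile of Beta(x+1, n−x). For 5/20 they are (0.0866, 0.4910) and for 6/24 (0.0977, 0.4671), which reproduce the Section 11 table. As a separate matter, Section 11 presents its example as a 20% rate, "based on 5 responses in 20 patients is (0.087, 0.491), with a precision of 0.185", but 5/20 is 25%. The half-width for 5/20 is (0.4910 − 0.0866)/2 = 0.202; 0.185 is the half-width for 6/24, (0.4671 − 0.0977)/2.

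**Step 4. What one event does.** The rule speaks of a difference but names no comparator, so I read it as an observed rate below 20%. That means at most 3 events in 20 patients or at most 4 in 24.

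| n | Before | After one event is removed |
|---|---|---|
| 20 | 4/20 = 20.0%, goal missed | 3/20 = 15.0%, 95% CI 0.032 to 0.379, goal met |
| 24 | 5/24 = 20.8%, goal missed | 4/24 = 16.7%, 95% CI 0.047 to 0.374, goal met |

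**Step 5. Illustration over a range.** The documents give neither a true in-field rate p nor a share m of events lost to the progression label, so both are assumptions. If each event is lost independently, the count is binomial with probability p(1−m). The chance of meeting the goal is P(X ≤ 3) for n = 20 and P(X ≤ 4) for n = 24.

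| p | n | m = 0 | m = 10% | m = 20% | m = 30% |
|---|---|---|---|---|---|
| 0.10 | 20 | 0.867 | 0.901 | 0.929 | 0.953 |
| 0.10 | 24 | 0.915 | 0.941 | 0.961 | 0.977 |
| 0.25 | 20 | 0.225 | 0.310 | 0.411 | 0.526 |
| 0.25 | 24 | 0.247 | 0.344 | 0.460 | 0.587 |
| 0.30 | 20 | 0.107 | 0.170 | 0.257 | 0.369 |
| 0.30 | 24 | 0.111 | 0.183 | 0.283 | 0.412 |

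Where in-field toxicity is rare the label changes little. Where the true rate is above the goal, even a modest share matters. The table shows sensitivity; it does not estimate what will happen.

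**The case against.** The strongest reply is that the clause exempts progression, not toxicity. A reader might infer that radiation or combination injury in the field generally disappears from the primary rate. The documents do not support that. Such injury is an adverse event under the general definition regardless of cause. Section 8 requires CTCAE-graded radiation toxicity evaluation at about 1 month and then every 3 months for at least a year, and the flow chart schedules grading of the irradiated site. All of this stands, and it is why the size of the loss is unknown.

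Nor is progression a free label. It is judged by IMWG criteria, and Section 5 allows apparent progression in the week 6 to 8 labs to be checked again 4 to 8 weeks later. This limits mislabelling, although the stated reason, atypical response patterns, concedes that early calls are uncertain, and weeks 6 to 8 fall within the 3-month window. Section 10 also has suspected progression reviewed and forwarded as a serious event if it proves to be something else. That is a useful check, but it governs reporting to the manufacturer and is not tied to the primary count.

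It is also tempting to say the bias can only be downward. The flow chart's note on irradiated-site grading lists no pre-treatment grade, although a general adverse event assessment is marked before treatment. Without a site reference, old pain could be counted as new toxicity, which would raise the rate.

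Finally, Section 2 defines acute toxicity as associated with radiation. Making an all-cause in-field count the primary endpoint would redefine it and bring in true progression. That objection stands, so the broader count belongs in a sensitivity analysis.

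**Conclusion.** The inconsistency is real and narrow. Both progression clauses are lifted only by a link to the drug, while the adverse event definition, the Section 8 attribution and the primary endpoint all involve radiotherapy. In-field worsening called progression and judged due to radiotherapy falls outside the adverse event definition and can leave the primary rate.

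The only size that follows from the documents is that a single event decides the verdict at the threshold, reading the rule as an observed rate below 20%. A reader of the Step 5 table might conclude that the chance of a false declaration of safety doubles. That needs a true rate above the goal and a sizeable relabelled share, and the documents give neither. At a true rate of 25% and n = 20, a 10% share moves the chance of meeting the goal from 0.225 to 0.310.

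I rate this a wording inconsistency with a possible downward bias. It is worth correcting but is not a must-fix.

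**What to change.** 1. In the progression exemption and in the exception to serious event reporting (both Section 10), replace the drug-only condition with *related to pembrolizumab, radiotherapy or their combination*. The first change bears on the primary rate. The second affects only reporting, and keeps the two clauses consistent.
2. Record the CTCAE grade of the irradiated site at the pre-treatment adverse event assessment already in the Section 9 flow chart, so that new or worsened events can be told from old ones.
3. Keep the primary endpoint as defined. In Section 11 add a sensitivity rate, with its Clopper-Pearson interval, that counts every new or worsened event above grade 2 at the irradiated site by 3 months, including events attributed to progression.

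The cost is two wording changes, one extra entry at an existing assessment and a little more analysis. The sensitivity rate may exceed the primary rate because it includes some true progression, and the report should say so. No treatment or visit changes.
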